11 SAFETY AND TOLERABILITY ANALYSIS

All safety analyses will be performed for participants in the safety analysis set.

The analysis of safety assessments in this study will include summaries of the following categories of safety and tolerability data collected for each subject:

- Treatment Emergent Adverse Events:
 - Clinical laboratory Treatment Emergent Adverse Events
 - Discontinuation due to TEAEs
 - Treatment Emergent Serious Adverse Events
- Pregnancies (if any reported)
- Clinical Laboratory Investigations
- Vital Signs
- Physical examinations

11.1 Adverse Events

Adverse events (AEs) will be coded using the Medical Dictionary for Regulatory Activities (MedDRA) central coding dictionary, version 25.0.

The incidence of treatment-emergent AEs (TEAEs, defined as AEs occurring from the time of first dose through 7 days after the last dose of MN-166), SAEs and AEs leading to discontinuations will be summarized by treatment group. Incidence of TEAEs will also be summarized by severity (mild, moderate, or severe), as well as by relationship to treatment (not related, possibly related, or probably related) and by seriousness. If it cannot be determined whether the AE is treatment emergent due to a partial onset date then it will be counted as such.

Summaries that are displayed by system organ class and preferred terms will be ordered by descending order of incidence of system organ class and preferred term within each system organ class. Summaries of the following types will be presented:

Confidential

- Subject incidence of TEAEs and total number of unique TEAEs by MedDRA system organ class and preferred term.
- Subject incidence of TEAEs by MedDRA system organ class, preferred term, and highest severity. At each level of subject summarization, a subject is classified according to the highest severity if the subject reported one or more events. AEs with missing severity will be considered severe for this summary.
- Subject incidence of TEAEs by MedDRA system organ class, preferred term, and closest relationship to study drug (Related/Not Related). At each level of subject summarization, a subject is classified according to the closest relationship if the subject reported one or more events. AEs with a missing relationship will be considered related for this summary.
- Subject incidence of serious TEAEs and total number of unique serious TEAEs by MedDRA system organ class and preferred term.
- Subject incidence of TEAEs leading to study discontinuation or death by MedDRA system organ class and preferred term.

As this is a double-blind study, the causality assessment should be made under the assumption that the subject is receiving active study medication. If considering unblinding, this assessment should be made prior to unblinding to avoid bias.

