6.0 SYNOPSIS

Name of Investigational Product: MN-166 (ibudilast)
Title of Study: A Randomized, Double-Blind, Placebo-Controlled, Parallel Group Study to Evaluate the Efficacy, Safety, Tolerability, Biomarkers and PK of ibudilast (MN-166) in COVID-19 Subjects at Risk for Developing Acute Respiratory Distress Syndrome (ARDS)
Study Number: MN-166-COVID-19-201
Study Phase: Phase 2
Study Center: Multicenter
Number of Subjects (Planned): Approximately 40 patients
FPI Date: Anticipated 4Q2020
Screening Phase: up to 3 days, Treatment Phase: 7 days, Follow-up Phase: Study Day 14, 28, and Day 60
Duration of Study Drug Treatment: 7 days
Study Treatments Test Drug: Ibudilast (MN-166) oral 50 mg bid Comparator Drug: Matching placebo oral 50 mg bid Study drug administration: Study drug will be administrated orally. If subject becomes dependent on a gastric tube, study drug can be given via gastric tube by opening the capsules in an enteral syringe, then suspend in 30 mL distilled water. If study drug is started on Day 1 in the PM, the last dose of study drug will be taken on Day 8 in the AM.
Duration of Subject Participation: Approximately 60 days
Study Design: This is a randomized (1:1) double-blind, placebo-controlled, parallel-group study of ibudilast in hospitalized COVID-19 subjects at risk for developing ARDS receiving standard of care including anticoagulation. The study will consist of a Screening Phase followed by a Treatment and Follow-up Phase. Following the Screening Phase, if the subject meets eligibility criteria, subject will be administered treatment with MN-166 (ibudilast) or placebo. Subjects will receive ibudilast 100 mg/d (50 mg b.i.d) or placebo every day for 7 days. Upon completion of the 7-day Treatment Phase, subject will be followed-up at Day 14, Day 28 and Day 60 post baseline.
Screening Phase (up to 3 days) The following screening assessments will be performed upon signing the ICF: inclusion/exclusion criteria review, physical examination, assess vital signs and O ₂ use and SpO ₂ , clinical status using the NIAID scale, ECG, draw blood for plasma cytokines that include migration inhibitory factor (MIF), (interleukin 1-beta (IL-1 β), interleukin 6 (IL-6), tumor necrosis factor (TNF α), C-reactive protein (CRP) and other exploratory biomarkers. Pharmacokinetic (PK) samples, complete blood count (CBC), comprehensive metabolic panel (CMP), D-dimer, and coagulation tests will also be

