12.7 Subject Stopping Criteria

A subject should be withdrawn from the study if any of the following abnormal lab values occur, **after repeat testing**:

- AST or ALT or total bilirubin $>3 \times$ upper limit of normal (ULN)
- Bilirubin $>3 \text{ mg/dL}$
- Serum albumin less than 28 g/L
- White blood count $<2500/\text{mm}^3$
- Platelet count $<75,000/\text{mm}^3$

A subject should also be withdrawn from the study if any of the following adverse events occur:

- Nausea considered moderate or severe and related to study drug by investigator for greater than 3 consecutive days despite maximal supportive therapy
- Vomiting considered moderate or severe and related to study drug by investigator for greater than 3 consecutive days despite maximal supportive therapy
- Diarrhea considered moderate or severe and related to study drug by investigator for greater than 3 consecutive days despite maximal supportive therapy
- Occurrence of an SAE or grade 3 adverse event related to study drug

Subjects who are withdrawn/discontinued from study drug to an abnormal lab result or adverse event will remain in the study and continue regularly scheduled efficacy and safety assessments.

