13.0 TREATMENTS

MN-166 (ibudilast) will be administered as MN-166 50 mg (5 capsules) b.i.d for 7 days. Study drug may be taken with food or within an hour of eating to improve gastrointestinal tolerability. Subjects who cannot tolerate a b.i.d. dosing regimen may be administered a t.i.d. dosing regimen (40 mg at breakfast, 30 mg at lunch, 30 mg dinner). Subjects who cannot tolerate this regimen will be discontinued from the study.

Day 1 study drug may be administered starting with the PM dose. If the first dose of study drug is administered in the PM then the last dose should be administered on Study Day 8 in the AM.

Matching placebo will also be provided and will be administered as 50 mg (5 capsules) b.i.d. for 7 days.

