16.0 SAFETY ASSESSMENTS

Adverse events (serious and non-serious) including all Suspected Unexpected Serious Adverse Reactions (SUSARs) should be collected from time of first dose of study drug until the end of their participation in the study (i.e., the subject has discontinued or completed the follow-up visit).

The PI or a qualified designee listed on Form FDA 1572 must assess the severity and relationship to study medication for all AEs.

The PI, sub-investigator (Sub-I) and members of the clinical research team are responsible for identifying adverse events and reporting them to the RN/study coordinator.

For all AEs, the Investigator must pursue and obtain information adequate to determine the outcome of the AE and to assess whether it meets the criteria for classification as an SAE requiring immediate notification to the Sponsor or its designated representative.

For all AEs, sufficient information should be obtained by the Investigator to determine the causality of the AE. The Investigator is required to assess causality and indicate that assessment on the CRF. For treatment-emergent AEs with a causal relationship to the investigational product, follow-up by the Investigator is required until the event or its sequelae resolve or stabilize at a level acceptable to the Investigator, and Sponsor concurs with that assessment.

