19.4 Safety Analysis

The incidence of treatment-emergent AEs (TEAEs, defined as AEs occurring from the time of first dose through 7 days after the last dose of study medication), SAEs and AEs leading to discontinuations will be summarized by treatment group. Incidence of TEAEs will also be

summarized by severity (mild, moderate, or severe), as well as by relationship to treatment (not related, possibly related, or probably related) and by seriousness.

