13.3 List of Tables

Table Number	Table Description
14.1	Demographic Data
14.1.1	Subject Disposition (including discontinued subjects)
14.1.2	Summary of Protocol Deviations
14.1.3	Demographics and Baseline Characteristics
	Summary of Disease Characteristics at Baseline by Treatment
14.1.4	Summary of Medical History
14.1.5	Prior and Concomitant Medications (Safety Population)
14.1.6	Study Drug Exposure
14.2	Efficacy
14.2.1	Number (%) of subjects free from respiratory failure at Day 7
14.2.2	Number (%) of subjects with at least a 1-point improvement in clinical status using the NIAID 8-point ordinal scale at Day 7
14.2.3	Number (%) of subjects free from respiratory failure at Days 14, 28, and 60
14.2.4	Number (%) of subjects with mechanical ventilation/intubation at Days 7, 14, 28, and 60
14.2.5	Change from baseline in clinical status using the NIAID 8-point ordinal scale at Days 7, 14, 28, and 60
14.2.6	Number (%) of subjects with at least a 1-point improvement in clinical status using the NIAID 8-point ordinal scale at Days 14, 28, and 60
14.2.7	Number (%) of subjects discharged from hospital at Days 7, 14, 28, and 60
14.2.8	All-cause mortality at Days 28 and 60
14.3	Safety
14.3.1	Summary of Treatment-emergent adverse events by Treatment
14.3.1.1	Incidence of TEAEs MedDRA System Organ Class and Preferred Term by Treatment
14.3.1.2	Incidence of TEAEs Occurring in more than 5% of Subjects by Treatment
14.3.1.3	Incidence of Post-treatment AEs by Treatment
14.3.1.4	Incidence of TEAEs by MedDRA System Organ Class, Preferred Term and Severity
14.3.1.5	Incidence of Treatment-Emergent Adverse Events by MedDRA System Organ Class, Preferred Term and Relationship to Study Drug
14.3.1.6	Incidence of Treatment-Emergent Adverse Events by MedDRA System Organ Class, Preferred Term, Relationship to Study Drug, and Severity
14.3.2	Incidence of Serious Treatment-Emergent Adverse Events by MedDRA System Organ Class and Preferred Term
14.3.3	Incidence of Serious Treatment-Emergent Adverse Events by MedDRA System Organ Class, Preferred Term and Severity
14.3.4	Incidence of Serious Treatment-Emergent Adverse Events by MedDRA System Organ Class, Preferred Term and Severity
14.3.4.1	Incidence of Subjects with Serious Treatment-Emergent Adverse Events by MedDRA System Organ Class, Preferred Term and Relationship
14.3.4.2	Incidence of Serious Treatment-Emergent Adverse Events by MedDRA System Organ Class, Preferred Term and Relationship

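### The serious-event tables stop counting 7 days after each subject's own last dose, so later non-fatal SAEs are listed but not counted as serious by arm

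*Combined protocol and SAP*

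**What the plan says.** SAP section 11.1 defines treatment-emergent events as those from first dose to 7 days after last dose: "defined as AEs occurring from the time of first dose through 7 days after the last dose of MN-166". Protocol section 19.4 uses the same rule but words it for both arms: "through 7 days after the last dose of study medication".

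Planned treatment lasts 7 days (protocol synopsis). Protocol section 13.0 puts the last dose on the morning of Day 8 when dosing starts in the evening of Day 1.

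Subjects taken off drug for a laboratory value or adverse event "will remain in the study and continue regularly scheduled efficacy and safety assessments" (protocol section 12.7; section 12.6 is similar). Protocol section 16.0 says that adverse events "should be collected from time of first dose of study drug until the end of their participation in the study".

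In the SAP, the serious-event summary in section 11.1, the overview in section 11.1.1 and Tables 14.3.2 to 14.3.4.3 in section 13.3 all cover treatment-emergent events only. The first of these tables is titled "Incidence of Serious Treatment-Emergent Adverse Events by MedDRA System Organ Class and Preferred Term". Section 11.1.3 provides a listing of SAEs without that limit. Section 11.1 also says that "SAEs and AEs leading to discontinuations will be summarized by treatment group", and gives no window for the SAEs it names there.

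**The concern.** Follow-up runs on after drug is stopped, but the counting window does not. Take a non-fatal SAE on Day 12. In a completer it is a serious treatment-emergent event and enters the serious-event tables. In a subject whose last dose was on Day 4 it falls outside the window and appears only in the SAE listing and, without a serious label, among post-treatment AEs.

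The length of the window is itself a result of treatment. Protocol section 12.7 makes persistent related gastrointestinal symptoms, specified laboratory values, and related SAEs or grade 3 events reasons to stop. If stopping differs between arms, the serious-event tables compare arms over unequal numbers of counted days. What is at stake is a clean by-arm count of non-fatal serious events in a trial whose stated aims include safety.

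**Working it through.** The plan states no event rate, stopping rate or sample-size calculation, so there is no figure of its own to reproduce. The window lengths follow from the text; the arm-level sizes are illustrations on stated assumptions.

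**1. Window by day of last dose.** The closing day is the day of last dose + 7.

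| Last dose | Window closes | Shortfall against a Day 7 finish |
|---|---|---|
| Day 1 | Day 8 | 6 days |
| Day 2 | Day 9 | 5 days |
| Day 4 | Day 11 | 3 days |
| Day 7 | Day 14 | none |
| Day 8 (evening start) | Day 15 | one day longer |

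**2. When stopping is plausible.** The gastrointestinal criteria need more than 3 consecutive days of symptoms (protocol 12.7), so the last dose is about Day 4 at the earliest. The first scheduled laboratory tests after baseline are on Day 3 (protocol 14.2), with a repeat within 24 hours before drug is stopped (protocol 13.5), so the last dose is about Day 3 or 4. A related SAE or grade 3 event could stop drug earlier. Day 4 is therefore the main case and Day 2 an extreme one.

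**3. Counted days, with assumed stopping of 20% on MN-166 and 5% on placebo.** Mean window = (1 − s) × 14 + s × closing day of the early stoppers.

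- Day 4 stops: MN-166 0.80 × 14 + 0.20 × 11 = 13.4; placebo 0.95 × 14 + 0.05 × 11 = 13.85. The ratio is 0.968, or 3.2% shorter.
- Day 2 stops: 0.80 × 14 + 0.20 × 9 = 13.0; 0.95 × 14 + 0.05 × 9 = 13.75. The ratio is 0.945, or 5% shorter.
- Days 10 to 14 alone, Day 4 stops (such a subject keeps Days 10 and 11): 0.80 × 5 + 0.20 × 2 = 4.4 against 0.95 × 5 + 0.05 × 2 = 4.85, or 9% fewer counted days.

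**4. Effect on the serious-event proportion.** Assume a constant daily SAE hazard h, equal in both arms, between 0.01 and 0.03. P(first SAE counted) = 1 − exp(−h × days). The distortion is the difference in stopping proportions times [exp(−h × closing day) − exp(−14h)]. Three assumed pairs of stopping proportions were used: 10% v 0%, 20% v 5% and 30% v 5%.

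| Last dose | h | Bracket | Distortion over the three pairs | Subjects per 20 |
|---|---|---|---|---|
| Day 4 | 0.01 | 0.0265 | 0.26 to 0.66 points | 0.05 to 0.13 |
| Day 4 | 0.03 | 0.0619 | 0.62 to 1.55 points | 0.12 to 0.31 |
| Day 2 | 0.01 | 0.0446 | 0.45 to 1.11 points | 0.09 to 0.22 |
| Day 2 | 0.03 | 0.1063 | 1.06 to 2.66 points | 0.21 to 0.53 |

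For example, Day 2 stops at 30% v 5% with h = 0.03 give 0.25 × 0.1063 = 2.66 points, and 20 × 0.0266 = 0.53 subjects.

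**5. What is reported by arm outside the window.** Table 14.3.1.3 gives post-treatment AEs, but its title does not split them by seriousness. Table 14.3.4.5 gives deaths. SAP sections 2.2.2 and 10.2 compare all-cause mortality at Days 28 and 60, and respiratory-failure status and ventilation at fixed days, with Day 60 limited to intubated subjects. SAP section 2.2.2 also names an AE endpoint at Days 7, 14, 28 and 60, but no table in section 13.3 is titled by fixed day. The remaining gap is later non-fatal events identified as serious.

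**6. How long the data run.** The SAP appendix reports 31 subjects consented under Amendment 2 and 5 under Amendment 4. As the Amendment 2 schedule reads in the available text, AE review ends at Day 14. For 31 of 36 subjects, then, the events at issue lie between about Day 8 and Day 14.

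**The case against.** Three stronger readings are tempting, and the documents support none of them.

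- A reader might infer that later serious events drop out of the arm comparison altogether. They do not: the by-arm outputs in step 5 remain. A respiratory failure on Day 12 that persists also shows in the Day 14 oxygen and ventilation comparisons, whenever drug was stopped.
- A reader might infer that early stoppers are observed for less time. They are not, because follow-up and AE collection continue; only the treatment-emergent label ends. This relies on the closing sentences of protocol sections 12.6 and 12.7. Both sections also speak of withdrawal from the study, and that wording must be reconciled.
- A reader might infer that the shortening favours ibudilast, because the protocol attributes gastrointestinal and liver-enzyme effects to the drug. That is plausible, but no stopping rate by arm is given, and the laboratory criteria apply to acutely ill subjects in both arms. The direction would reverse if placebo subjects stopped more often.

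It can also be said that last dose plus 7 days is a conventional window used consistently in both documents, and that the SAP sentence on summarising SAEs by treatment group may mean all SAEs. The first part stands: the rule need not be replaced. The second is a possible reading, but SAP section 11 names only treatment-emergent serious events among its safety summaries, and section 13.3 contains no all-SAE table to carry it out.

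The reference to MN-166 would, taken literally, leave placebo subjects without a window. The protocol's wording and the by-group summary show that this is a slip, with no likely effect on the analysis.

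**Conclusion.** The point holds in a limited form. The counting window is tied to each subject's own last dose, every serious-event table uses it, and later non-fatal SAEs therefore have no planned by-arm count as serious. A difference between arms is possible because stopping depends on tolerability and laboratory values, but its direction is not known.

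The size is small: about 0.05 to 0.3 of a subject per arm of 20 with Day 4 stops, and 0.1 to 0.5 with Day 2 stops. These figures rest on assumed stopping proportions, an assumed constant and equal SAE hazard, and arms of 20 from the planned total of about 40. This is an inexpensive improvement to the safety reporting and does not affect the efficacy analysis.

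**What to change.** - Keep the last-dose-plus-7 rule for treatment-emergent events.
- Add to SAP sections 11.1 and 13.3 one by-arm table of all SAEs in every dosed subject, from first dose over a common period, regardless of when drug was stopped: through the Day 14 visit for all, and through Day 28 where AEs are collected.
- In the SAP 11.1 definition, refer to the last dose of study drug instead of MN-166.

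The cost is one extra table and a small wording change, with no new data. The Day 14 visit has a window of ±3 days, so the end of the common period will vary slightly between subjects; the table should say so in a footnote.

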16.5 Recording Adverse Events

Adverse events should be collected and recorded for each subject from the date the patient receives study drug until the end of their participation in the study, (i.e., the subject has discontinued or completed the study) through the follow-up visit.

Adverse events may be volunteered spontaneously by the study subject, or discovered by the study staff during physical examinations or by asking an open, non-leading question such as, "How have you been feeling since you were last asked?" All AEs and any required remedial action will be recorded in the subject's source documentation and transcribed onto the appropriate CRF page for the study period indicated. The nature of AE, date (and time, if known) of AE onset, date (and time, if known) of AE outcome to date, severity, and action taken of the AE will be documented together with the PI's or an authorized physician's assessment of the

seriousness of the AE and causal relationship to study medication and/or study procedure (at the time of assessment).

All AEs should be recorded individually in the study subject's own words (verbatim) unless, in the opinion of the PI or an authorized physician, the AEs constitute components of a recognized condition, disease, or syndrome. In the latter case, the condition, disease, or syndrome should be named rather than each individual symptom. The AEs will subsequently be coded using the most current version of MedDRA.

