11.1.1 All Adverse Events

An overview of number of participants (%) with treatment-emergent AEs will be presented for the main AE categories (All AEs, AEs leading to discontinuation, SAEs, SAEs leading to discontinuation, AEs with at least Grade 3 severity (Severe AEs, Life-threatening AEs, Deaths), AEs and SAEs with relationship to IMP as possibly related, probably related, or related) by treatment arm and phase.

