11.1.2 Adverse Events Leading to Withdrawal

A data listing of AEs leading to withdrawal will be provided, displaying details of the event(s) captured on the CRF.

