14.3.4.3	Incidence of Serious Treatment-Emergent Adverse Events by MedDRA System Organ Class, Preferred Term, Relationship and Severity
14.3.4.4	Incidence of TEAEs Leading to Early Termination by Treatment

Confidential

14.3.4.5	Incidence of Deaths by Treatment
14.3.4.6	Incidence of TEAEs by Maximum Severity by Treatment
14.3.4.7	Summary of Clinical Laboratory Data: Clinical Chemistry by Treatment
14.3.4.8	Summary of Clinical Laboratory Data: Clinical Hematology by Treatment
14.3.4.9	Shifts from Baseline of Clinical Laboratory Data: Clinical Chemistry – Shift from Baseline to the Last Visit
14.3.4.10	Shifts from Baseline of Clinical Laboratory Data: Clinical Hematology by Treatment

Confidential

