13.4 List of Listings

Listing Number	Listing Description
16.2	Subject Data Listings
16.2.1	Analysis Populations and Treatment
16.2.1.1	Subject Disposition
16.2.1.2	Inclusion/Exclusion Criteria
16.2.2	Protocol Deviations
16.2.2.1	Major and Minor Protocol Deviations
16.2.2.3	Randomization Errors
16.2.3.1	Demographics and Other Baseline Characteristics
16.2.4	Prior, Concomitant, and Post-treatment Medications
16.2.4.1	Medical History
16.2.5	Study Drug Exposure
16.2.5.1	Drug Accountability and Compliance
16.2.5.2	Investigator Dose Optimization
14.2.5.3	Dose Interruptions
16.2.6	Individual Response Efficacy
16.2.6.1	NIAID clinical status 8-point ordinal scale
16.2.6.2	O2 assessment including invasive mechanical ventilation, non-invasive ventilation (CPAP, BiPAP, nasal cannula high-flow oxygen), or ECMO and SpO2
16.2.6.3	Day of Hospital Discharge
16.2.6.4	Survival Status
16.2.7	Individual Safety
16.2.7.1	Adverse Events
16.2.7.2	Serious Adverse Events
16.2.7.3	Adverse Events Leading to Early Termination
16.2.7.4	Listing of Deaths
16.2.8	Listing of Individual Laboratory Measurements by Subject, when Required by Regulatory Authorities
16.2.8.1	Clinical Laboratory Data: Chemistry
16.2.8.2	Clinical Laboratory Data: Hematology
16.2.8.3	Pregnancy Tests
16.2.8.4	Vital Signs
16.2.8.5	Electrocardiogram, Site Interpretation
16.2.8.6	Electrocardiogram, Central Reader Interpretation
16.2.8.7	Physical Examination

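### Three SAP safety outputs count AEs that lead to leaving the study, so they can miss AEs that led subjects to stop study drug while staying in follow-up

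*Combined protocol and SAP*

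**What the plan says.** **Outputs tied to leaving the study.** The SAP 11.1 summary by system organ class and preferred term is "Subject incidence of TEAEs leading to study discontinuation or death by MedDRA system organ class and preferred term". SAP 13.3 gives Table 14.3.4.4 as "Incidence of TEAEs Leading to Early Termination by Treatment", and SAP 13.4 gives Listing 16.2.7.3 as "Adverse Events Leading to Early Termination".

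**Outputs that do not say whether drug or study is meant.** The general sentence in SAP 11.1 promises that "SAEs and AEs leading to discontinuations will be summarized by treatment group". The overview in SAP 11.1.1 has rows for "All AEs, AEs leading to discontinuation, SAEs, SAEs leading to discontinuation". SAP 11.1.2 states that "A data listing of AEs leading to withdrawal will be provided". SAP 11 also lists discontinuation due to TEAEs among its safety categories, without further definition.

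**What the protocol says about subjects who stop drug.** Protocol 12.7 says that subjects taken off drug for an abnormal laboratory result or an adverse event "will remain in the study and continue regularly scheduled efficacy and safety assessments". Protocol 12.6 says the same of subjects taken off drug for any reason other than loss to follow-up or withdrawn consent. Protocol 13.5 continues the scheduled tests while dosing is withheld for a confirmed laboratory abnormality.

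**What is recorded.** Protocol 16.5 states that for each AE the "severity, and action taken of the AE will be documented". Protocol 12.6 has the reason and date of stopping study medication entered on the CRF.

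**The concern.** Safety and tolerability is a stated objective (protocol 10.2, SAP 2.1.2). In a seven-day oral regimen, stopping the drug because of an adverse event is one of the most direct measures of tolerability. The protocol's own history points to the events that matter: section 9.1 describes a suggested dose-related increase in nausea and transient changes in AST, ALT and GGT, and section 12.7 has gastrointestinal and laboratory criteria. Protocol 12.8 treats safety-driven stopping of treatment as a trial-level signal, since two such subjects trigger a temporary halt in dosing.

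If the outputs that break these events down by term and arm are keyed to leaving the study, a subject who stops drug for nausea and completes follow-up does not appear in them. The report could then show few or no AE-related discontinuations although several subjects could not continue the drug. SAP 1 makes the SAP authoritative on data analysis, so its wording is what the programmer will follow.

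**Working it through.** The documents contain no figure to reproduce, so the check is mainly a comparison of texts.

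**Step 1. Follow one subject through the outputs.** Take a subject who permanently stops drug for an AE, stays in follow-up as the second part of protocol 12.7 describes, and completes the study.

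| SAP output | Event that qualifies | Is the subject counted? |
|---|---|---|
| 11.1 summary by SOC and preferred term | study discontinuation or death | No, read literally |
| Table 14.3.4.4 | early termination | No, read literally |
| Listing 16.2.7.3 | early termination | No, read literally |
| 11 and 11.1 general text; 11.1.1 overview rows | discontinuation, undefined | Depends on programming |
| 11.1.2 listing | withdrawal, undefined | Depends on programming |
| Table 14.1.6; exposure, compliance and dose-interruption listings | dosing | The stop may be visible, but not as incidence by AE term and arm |

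SAP 13.4 has no listing with withdrawal in its title. The nearest to the one promised in 11.1.2 is Listing 16.2.7.3, which uses early termination.

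**Step 2. Test whether the subject really stays in the study.** The protocol gives two answers.

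- Remains in the study: last part of 12.6, end of 12.7, and 13.5.
- Leaves the study: 12.6 lists AEs that require stopping study medication among the cases for study withdrawal; 12.7 opens both its laboratory and its AE criteria with withdrawal from the study; 13.0 discontinues from the study those who cannot tolerate the alternative regimen.

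Under the first answer the three outputs miss the subject. Under the second they capture the subject. The same drug stop can therefore be tabulated or not, depending on how each of the two centers (SAP 7.4) recorded it.

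**Step 3. Scale.** SAP 13.1 and 13.2 give 31 + 5 = 36 consented. If all were randomized and split evenly (an assumption), that is 36/2 = 18 per arm. The planned size of about 40 gives 40/2 = 20 per arm. One missed subject is 1/18 = 5.6% or 1/20 = 5.0% of an arm.

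The documents give no drug-stop rate, so p is assumed over a range. The formulas are P(at least one) = 1 − (1 − p)^n and P(at least two) = 1 − (1 − p)^n − n·p·(1 − p)^(n−1).

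| Assumed p | n = 18: at least one | n = 18: at least two | n = 20: at least one | n = 20: at least two |
|---|---|---|---|---|
| 5% | 60% | 23% | 64% | 26% |
| 10% | 85% | 55% | 88% | 61% |
| 20% | 98% | 90% | 99% | 93% |

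For example, with n = 18 and p = 0.10, 1 − 0.9^18 = 0.85. These are chances that an arm contains such subjects. Whether they are missed depends on Step 2.

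**The case against.** **The protocol may treat these subjects as having left the study.** Protocol 12.6, 12.7 and 13.0 all contain wording to that effect, and stopping for nausea is one of the cases that 12.7 introduces as study withdrawal. If the sites worked that way, the outputs would capture the events. This stands as a limit on certainty. It does not remove the problem, because the same sections also say the opposite and the SAP does not choose between them.

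**Other outputs exist.** The 11.1.1 overview gives counts by arm for AEs leading to discontinuation, 11.1.2 promises a listing, and Listing 16.2.7.1 covers all adverse events. With about 40 subjects, case-by-case reading is feasible. This also stands in part. A reader might infer that no planned output will show drug stops, or that the three explicit outputs define the loose terms elsewhere. The documents do not support that: nothing in the SAP ties the bare terms to study exit.

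**The deaths argument.** A reader might also infer that merging deaths into the 11.1 summary makes it track disease and favour the drug. For example, with 18 per arm, assume 3 ibudilast and 0 placebo drug stops with follow-up completed, and 1 and 2 fatal TEAEs. The merged count is then 1/18 (5.6%) against 2/18 (11.1%), while AE-driven drug stops are 3/18 (16.7%) against 0/18. Those counts are invented, and the reversal shows only in a pooled total. The summary is by organ class and term, so gastrointestinal and fatal respiratory events fall in different rows. Table 14.3.4.5 reports deaths separately. Fatal events that start more than 7 days after the last dose are not TEAEs. No directional bias is shown.

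**Reach.** Of the 36 consented, 31 entered under Amendment 2, whose discontinuation text is not in the file. The remain-in-study wording is confirmed only for Amendment 4, under which 5 consented. This stands.

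**Conclusion.** The point holds in a limited form. The 11.1 summary by organ class and preferred term, Table 14.3.4.4 and Listing 16.2.7.3 can miss AE-driven discontinuations of study drug. The omission is certain only for those three, and only where a subject who stopped drug was kept in the study. For the remaining outputs the defect is an undefined term, not a proven loss.

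No count of missed events can be given, because the documents state no drug-stop rate. In arms of 18 to 20, one or two subjects are enough to change what the table says about tolerability. The efficacy tests, the significance level and the sample size are unaffected.

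The conclusion assumes that the SAP is programmed as written and that the remain-in-study sentences were followed. It is confirmed for Amendment 4 only. Protocol 12.6, 12.7 and 13.0 contradict themselves or each other on whether these subjects leave the study, and must be reconciled. This review takes no view on which rule is right.

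**What to change.** 1. In SAP 11.1 and 11.1.1, define AEs leading to discontinuation as AEs leading to permanent discontinuation of study drug. Derive this from the reason and date of drug discontinuation (protocol 12.6) and the AE action taken (protocol 16.5). The CRF is not in the file, so confirm that the action-taken field has an option for stopping study drug. If it does not, rely on the reason and date.
2. Add one table by arm, organ class and preferred term, and one listing, on that definition.
3. Keep TEAEs leading to study withdrawal as a separate summary. It should not be replaced: dosing ends on Day 7 or the morning of Day 8, the TEAE window runs 7 days further, and an AE that causes study exit after the last dose has no drug action and would drop out of a drug-only table.
4. Report fatal TEAEs separately from both.
5. In Table 14.1.1, show study-drug discontinuation with its reason, including laboratory criteria, apart from study withdrawal.
6. State in SAP 11.1.2 which kind of withdrawal its listing covers and which listing number delivers it.
7. Reconcile protocol 12.6, 12.7 and 13.0, and state which discontinuation text applied to subjects consented under Amendment 2.

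The cost is SAP wording, one extra table and one extra listing. If the CRF fields are as the protocol describes, no new data are needed.
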